## 5.2. Method of Assignment to Treatment

Patients who meet all criteria for enrollment will be randomized in a 1:1:1 ratio (placebo; baricitinib 2 mg; baricitinib 4 mg) to double-blind treatment at Visit 2 (Week 0). Randomization will be stratified by geographic region (Europe [EU], Japan [JPN], rest-of-world [ROW]) and disease severity at baseline (IGA 3 vs. 4). Assignment to treatment groups will be determined by a computer-generated random sequence using an IWRS. The IWRS will be used to assign packages containing double-blind investigational product tablets to each patient according to the study schedule of activities. Site personnel will confirm that they have located the correct packages by entering a confirmation number found on the packages into the IWRS.

This study will be conducted internationally in multiple sites. [Table JAIY.5.1](#) describes how regions will be defined for stratification. Regions may be combined for statistical analyses in the

case when one of the region strata fails to meet the required minimum number of 30 patients. The 2 region strata with the least number of patients will then be pooled.

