### **6.2.3. Analysis Methods**

The main analysis method of categorical efficacy variables and health outcomes variables will use a logistic regression analysis with region, baseline disease severity (IGA), baseline value and treatment group in the model, except for the analysis on IGA. For IGA, the logistic regression model will include region, baseline disease severity (IGA), and treatment group. Firth's correction will be used in order to accommodate (potential) sparse response rates. The p-value for the odds ratio from the logistic regression model will be used for statistical inference, unless Firth's correction still results in quasi-separation. In that case, Fisher's exact test will be used for statistical inference. The difference in percentages and 100(1-alpha)% CI of the difference in percentages using the Newcombe-Wilson method without continuity correction will be reported. The p-value from the Fisher's exact test will also be produced as a secondary analysis.

The main analysis method for all continuous efficacy and health outcomes variables will use mixed model repeated measures (MMRM) analysis. The MMRM model will use a restricted maximum likelihood (REML) estimation. The model will include treatment, region, baseline disease severity (IGA), visit, and treatment-by-visit-interaction as fixed categorical effects and baseline and baseline-by-visit-interaction as fixed continuous effects. For daily diary assessments, the model for analyses up to Week 16 will include all weekly assessments. An unstructured (co)variance structure will be used to model the between- and within-patient errors. If this analysis fails to converge, the heterogeneous autoregressive [ARH(1)], followed by the heterogeneous compound symmetry (CSH), followed by the heterogeneous Toeplitz (TOEPH), followed by autoregressive [AR(1)], followed by compound symmetry (CS) will be used. The

Kenward-Roger method will be used to estimate the degrees of freedom. Treatment least squares means (LSM) will be estimated within the framework of the MMRM using type 3 sums of squares. Differences in LSM between each dose of baricitinib and placebo (and associated p-values, standard errors and 95% CI) will be used for statistical inference. The LSM difference, standard error, p-value and 95% CI will be reported.

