Treatment comparisons for continuous efficacy and health outcomes variables may also be made using analysis of covariance (ANCOVA) for primary and key secondary objectives. When an ANCOVA model is used, the model includes region, baseline disease severity, treatment group, and baseline value. Treatment LSM will be estimated within the framework of the ANCOVA using type 3 sums of squares. Reported differences in LSM and associated p-values, standard errors and 95% CI will be used for statistical inference. Treatment-by-region interaction will also be added to the model for sensitivity purposes and is discussed in Section 6.5.

Beginning on Day 14 a Cox proportional hazard (CPH) model of time (in days) to first observance of a 4-point itch reduction with effects for treatment, region, baseline mean itch, and disease severity will be used to test for treatment differences from placebo. For this analysis, daily itch scores will be compared to the baseline to determine if a 4-point itch reduction has been achieved in patients with a baseline itch of at least 4. The baseline for Itch NRS is defined in Section 6.2.2. Beginning on Day 14, the day on which the first time itch NRS is reduced by at least 4 will be modeled. If any significant difference between any baricitinib dose and placebo is observed then the same analyses will be run on Day 13. This process of evaluating at the next lowest day will proceed until no significant differences are observed. No adjustments for multiple tests and multiple comparisons will be used. This analysis uses the Primary Censoring Rule for patients who are rescued or permanently discontinue study drug (see Section 6.4). Missing daily itch data will be replaced using NRI rule which means missing data is replaced with a non-response which would entail replacing missing values with a time to event of >14 days, censored; >13 days, censored, etc., depending on the window being used. If the model assumptions for the CPH model do not hold, a log-rank test will be used.

Restricted mean survival time will be evaluated at Days 2, 3, 4 and 5 as an exploratory analysis. The model will include terms for baseline disease severity (IGA), baseline itch, region, and treatment group.

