### 6.3. Covariate Adjustment

The randomization to treatment groups at Week 0 (Visit 2) is stratified by disease severity (IGA) and geographic region as described in Section 5.1. Unless otherwise specified, the statistical analysis models will adjust for these stratification variables. The covariates used in the logistic model for categorical data will include the parameter value at baseline. The covariates used in the ANCOVA model for continuous data will include the parameter value at baseline. Inclusion of baseline in the model ensures treatment LSM are estimated at the same baseline value. When an MMRM analysis is performed, baseline value and baseline-by-visit interactions will be included as covariates.

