a PIQ – Itch Interference here is the same as PIQ – General in the protocol.

Table JAIY.6.7. Description of Health Outcomes and Quality-of-Life Measures Analyses

Measure	Variable	Analysis Method (Section 6.2.3)	Population (Section 6.2.1)	Comparison/Time Point	Analysis Type
Itch Numeric Rating Scale (NRS)	
 
Itch NRS score
 
Change from baseline in Itch NRS score
 
	MMRM	ITT	Bari 4 mg or Bari 2 mg vs PBO; Week 1, ..., 16	Secondary Analysis
		ANCOVA using mLOCF	ITT	Bari 4 mg or Bari 2 mg vs PBO; Day 2, Week 1, ..., 16	Secondary Analysis at Day 2; Sensitivity Analysis for others
		pMI	ITT	Bari 4 mg or Bari 2 mg vs PBO; Week 1, ..., 16	Sensitivity Analysis
	Percent change from baseline Itch score	MMRM	ITT	Bari 4 mg or Bari 2 mg vs PBO; Week 1, ..., 16	Secondary Analysis
		ANCOVA using mLOCF	ITT	Bari 4 mg or Bari 2 mg vs PBO; Day 2, Week 1, ..., 16	Secondary Analysis at Day 2; Sensitivity Analysis for others
	Proportion of patients achieving a 4-point improvement in Itch NRS in subgroup of patients who had baseline Itch NRS $\geq 4$	Logistic regression using NRI	ITT	Bari 4 mg or Bari 2 mg vs PBO; Day 2, Week 1, ..., 16	Key Secondary Analysis at Day 2, Week 1, 2 and 16
			PPS	Bari 4 mg or Bari 2 mg vs PBO; Week 16	Sensitivity analysis
		Logistic regression using pMI and Tipping Point	ITT	Bari 4 mg or Bari 2 mg vs PBO; Week 16	Sensitivity analysis
	Number of Itch-free (Itch NRS = 0) Days	Two-sample t-test	ITT	Bari 4 mg or Bari 2 mg vs PBO; Week 0 to Week 4, ..., Week 12 to 16	Exploratory Analysis
	Skin Pain Numeric Rating Scale (NRS)	
 
Skin Pain NRS score
 
Change from baseline in Skin Pain NRS score
 
	MMRM	ITT	Bari 4 mg or Bari 2 mg vs PBO; Week 1, ..., 16
PPS				Bari 4 mg or Bari 2 mg vs PBO; Week 1, ..., 16	Sensitivity analysis

Measure	Variable	Analysis Method (Section 6.2.3)	Population (Section 6.2.1)	Comparison/Time Point	Analysis Type
		ANCOVA using mLOCF	ITT	Bari 4 mg or Bari 2 mg vs PBO; Week 1,..., 16	Sensitivity Analysis
		pMI	ITT	Bari 4 mg or Bari 2 mg vs PBO; Week 1,..., 16	Sensitivity analysis
	Number of Skin Pain-free (Skin pain NRS = 0) Days	Two-sample t-test	ITT	Bari 4 mg or Bari 2 mg vs PBO; Week 0 to Week 4,..., Week 12 to 16	Exploratory Analysis

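### Itch-free and skin pain-free days (exploratory) get an unadjusted t-test where comparable SAP analyses adjust for region and IGA: a valid test that may lose some precision

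*SAP*

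**What the plan says.** SAP Table JAIY.6.7 has one row for "Number of Itch-free (Itch NRS = 0) Days" and one for "Number of Skin Pain-free (Skin pain NRS = 0) Days". For each, the only method listed is "Two-sample t-test". Each baricitinib dose is compared with placebo in the ITT population over four 4-week intervals, and the analysis is labelled exploratory. No covariate is named.

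The rest of the plan points towards adjustment:

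- Section 5.2: "Randomization will be stratified by geographic region (Europe [EU], Japan [JPN], rest-of-world [ROW]) and disease severity at baseline (IGA 3 vs. 4").
- Section 6.3: "Unless otherwise specified, the statistical analysis models will adjust for these stratification variables".
- Section 6.2.3: "The main analysis method for all continuous efficacy and health outcomes variables will use mixed model repeated measures (MMRM) analysis". On covariates it adds: "The model will include treatment, region, baseline disease severity (IGA), visit, and treatment-by-visit-interaction as fixed categorical effects". Baseline score and its interaction with visit enter as continuous effects.
- Section 6.2.3, for cases where ANCOVA is used: "the model includes region, baseline disease severity, treatment group, and baseline value".

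The method column of Table JAIY.6.7 refers to Section 6.2.3, but that section describes no t-test.

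**The concern.** These two rows stand apart from their neighbours, and the plan does not say why. Exploratory status does not explain it. The PIQ scores are exploratory and use the adjusted MMRM, Neuro-QoL is exploratory and uses ANCOVA, and the exploratory restricted mean survival time analysis of itch includes IGA, baseline itch and region. The Patient Benefit Index is exploratory and has no baseline term, yet it still uses an ANOVA with region and IGA. The closest analogue, days without background TCS, is also a count of diary days and is analysed by ANOVA with region and severity.

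The covariates are already available. Region and IGA are randomisation strata, and the Itch NRS and Skin Pain NRS baselines are 7-day diary means (SAP Section 6.2.2). It is plausible, though the documents do not show it, that a patient who starts with worse itch or pain reports fewer zero-score days. If so, an unadjusted comparison leaves explainable variation in the error term and the intervals are wider than they need be. Precision on 16 exploratory comparisons is at stake (2 endpoints × 2 doses × 4 intervals), and nothing in the confirmatory testing.

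**Working it through.** **The plan's own figure.** No power or precision is stated for the day counts. The only power figure, 89% for the primary endpoint (10% vs 30%, 100 per arm, Fisher exact test, 2-sided alpha 0.025; Protocol Section 10.1, SAP Section 6.1), reproduces at 89.1% by exact enumeration. It does not bear on this point, except that 100 per arm is used below.

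**Inputs.** From the documents: 100 per arm; 2-sided 0.05 with no multiplicity adjustment for these endpoints (SAP Sections 6.2 and 6.6); candidate covariates region, baseline IGA and baseline NRS. Assumed: R², the share of variance in the day count that these covariates explain. The documents do not give it, so a range is shown.

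**Formulas.**

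- SE ratio, adjusted to unadjusted = √(1 − R²).
- Equivalent unadjusted sample size per arm = 100 / (1 − R²).
- Power of the adjusted model, for an effect that the t-test detects with 80% power = Φ(2.802/√(1 − R²) − 1.960), where 2.802 = 1.960 + 0.842.

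| R² (assumed) | SE ratio | SE reduction | Equivalent n per arm | Power (t-test 80%) |
|---|---|---|---|---|
| 0.01 | 0.995 | 0.5% | 101 | 80.4% |
| 0.05 | 0.975 | 2.5% | 105 | 82.0% |
| 0.10 | 0.949 | 5.1% | 111 | 84.0% |
| 0.20 | 0.894 | 10.6% | 125 | 87.9% |

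**Check with skewed counts.** The formula was checked by simulating a skewed count of 0 to 28 days, with 100 per arm, allocation balanced within strata and 1,500 trials per scenario. The simulation inputs are invented, so only the comparison between the two methods is informative.

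| R² in the simulation | SE, t-test | SE, adjusted | Power, t-test | Power, adjusted |
|---|---|---|---|---|
| 0.009 | 0.838 | 0.837 | 81.4% | 81.6% |
| 0.065 | 0.853 | 0.826 | 78.5% | 81.9% |
| 0.193 | 0.921 | 0.829 | 69.2% | 77.0% |

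With no treatment effect, the t-test rejected in 4.4% to 5.5% of trials and the adjusted model in 4.9% to 5.9%. The t-test therefore holds its level, and the difference between the methods is one of efficiency. With weak covariates there is in effect no gain.

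**The case against.** The strongest reply is that the plan permits this. Section 6.3 allows exceptions where another method is specified, and the table specifies one. The ANCOVA sentence in Section 6.2.3 applies only when ANCOVA is used, and ANCOVA is offered there as an option for primary and key secondary objectives. A count of 0 to 28 days might also not be meant by a continuous variable. This stands as far as permission goes: a reader might infer a breach of the SAP's own rule, and the wording does not support that. It still leaves the statement in Section 6.2.3 about all continuous outcomes unreconciled with these rows, and it gives no reason for the exception.

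Other stronger readings also fail:

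- **Bias or inflated Type I error.** A reader might infer this from ignoring the strata. Treatment is randomised, and the simulated rejection rates stay close to 5%.
- **Every other continuous analysis uses both strata and the baseline score.** It does not. The TCS and Patient Benefit Index ANOVAs use strata without a baseline score, and the safety ANCOVAs use baseline without strata.
- **A definite loss of precision.** The size depends on an R² that the documents do not give, and it may be near zero.
- **Harm to the study's aim on patient-reported itch.** That aim rests on the multiplicity-controlled 4-point Itch NRS endpoints, which are analysed with covariates. The day counts are outside the testing procedure.

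The reply is also right that adjustment has a small cost. Under Section 6.2.2 the diary baseline is missing when fewer than 4 assessments are available even after the window is extended. The day count needs no baseline, so a complete-case ANCOVA would drop patients whom the t-test keeps.

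**Conclusion.** The point holds as a minor matter of efficiency and consistency. The two t-test rows are unadjusted without a stated reason, while the plan's general method for continuous health outcomes is adjusted and its nearest comparable analyses include region and IGA. The expected gain from adjustment is a standard error lower by about 0.5% to 10.6%, if the covariates explain 1% to 20% of the variance. That range is assumed, and the simulation suggests that the gain at the bottom of it is even smaller than the formula gives. The t-test remains valid, both endpoints are exploratory, and no primary or key secondary conclusion is affected.

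**What to change.** In both rows of Table JAIY.6.7, replace the t-test with a linear model for each 4-week interval, with treatment, region, baseline IGA and the matching baseline score (Itch NRS for itch-free days, Skin Pain NRS for pain-free days). Add a rule that keeps patients without a valid diary baseline in the model, for example a missing-baseline indicator or single mean imputation of the covariate. Alternatively, adjust for region and IGA only, as for days without background TCS. That needs no baseline score and loses no patients, but gives up whatever the baseline score would explain.

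The cost is an edit to two table rows and one sentence on missing baselines. No new data are needed. If the sponsor prefers to keep the t-test, one sentence should say why these rows depart from Section 6.2.3, and that section should mention the test.

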## 6.14. Bioanalytical and Pharmacokinetic/Pharmacodynamic Methods

Pharmacokinetic (PK), Pharmacodynamic (PD) and Biomarker analyses to address secondary and exploratory objectives of this study will be described by Lilly in separate PK/PD and Biomarker analysis plans.

## 6.15. Safety Analyses

The general methods used to summarize safety data, including the definition of baseline and postbaseline are described in Section 6.2.

Safety analyses will include data from first dose of the study treatment to after rescue, unless otherwise stated, and patients will be analyzed according to the investigational product to which they were randomized at Visit 2. A sensitivity approach to the safety analyses will use data censored at last dose of the study drug for patients rescued to systemic therapy. These analyses will be conducted for treatment-emergent adverse events (TEAEs), serious adverse events (SAEs), AEs leading to permanent study drug discontinuation and special topics excluding deaths and malignancies. Additional analyses may be conducted using data after rescue to systemic therapy for some safety topics such as systemic TEAEs, and SAEs. Safety analyses will use the safety population defined in Section 6.2.1.

Safety topics that will be addressed include the following: AEs including TEAEs and SAEs, clinical laboratory evaluations, vital signs and physical characteristics, Columbia Suicide Severity Rating Scale (C-SSRS), the Self-Harm Supplement Form, safety in special groups and circumstances, including adverse events of special interest (AESI) (see Section 6.15.5), and investigational product interruptions.

Unless otherwise specified, by-visit summaries will include planned on-treatment visits. For tables that summarize events (such as AEs, categorical lab abnormalities, shift to maximum value), post-last dose follow-up data will be included. Follow-up data is defined as all data occurring up to 30 days (planned maximum follow-up time) after last dose of treatment including rescue, regardless of study period.

For selected safety assessments other than events, descriptive statistics may be presented for the last measure observed during post-treatment follow-up (up to 30 days after the last dose of treatment including rescue, regardless of study period).

